All participants will receive SC infusions of pegcetacoplan or matching volumes of placebo twice weekly. All adult participants (regardless of weight), and adolescent participants who weigh at least 50 kg, will receive 20-mL SC infusions. Adolescent participants who weigh at least 35 kg but less than 50 kg will receive a reduced infusion volume (12 mL for the first infusion and 15 mL for each infusion thereafter). Adolescent participants who weigh at least 30 kg but less than 35 kg will receive a further reduced infusion volume (10 mL for the first 2 infusions and 12 mL twice weekly thereafter), as presented below. Study drug will be self-administered by the participant or administered by their caregiver, after receiving appropriate training and sign-off by a research nurse or other qualified personnel in their first treatment week.

Planned Dosing Regimens

Weight	First dose (infusion volume)	Second dose (infusion volume)	Maintenance dose (infusion volume)
All adult participants, adolescent participants ≥50 kg	1080 mg (20 mL)	1080 mg (20 mL)	1080 mg twice weekly (20 mL)
Adolescent participants 35 to <50 kg	648 mg (12 mL)	810 mg (15 mL)	810 mg twice weekly (15 mL)
Adolescent participants 30 to <35 kg	540 mg (10 mL)	540 mg (10 mL)	648 mg twice weekly (12 mL)

Duration of Participation:

Total participation will be 70 weeks (screening: 10 weeks; RCP: 26 weeks; open-label period: 26 weeks; follow-up: 8 weeks). Depending on treatment assignment, treatment with pegcetacoplan will be for a maximum of 52 weeks (RCP: 26 weeks; open-label period: 26 weeks).

Statistical Methodology:

Efficacy:

Primary Efficacy:

The targeted treatment regimen to be used for this study is pegcetacoplan or placebo plus stable regimen for C3G/IC-MPGN treatment. The primary estimand on the treatment effect of pegcetacoplan is for the participant population as defined through the study inclusion/exclusion criteria, with the primary endpoint based on the log-transformed ratio of uPCR (sampled from first-morning urine collections) at week 26 compared to baseline using an equal-weighted average over weeks 24, 25, and 26. Intercurrent events (ICEs) will be addressed as defined in Table 8.

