6.1.3. Part 3: Open-Label Period (26 Weeks)

At the end of the RCP, participants from both groups will proceed to the 26-week open-label period, in which all participants will be treated with pegcetacoplan twice weekly. Open-label dosing will begin at the first visit after the week 26 renal biopsy for adults and any adolescents providing renal biopsies. Open-label dosing for adolescents not providing renal biopsies should start at the week 26 visit. At the end of the open-label period, there will be an optional renal biopsy. Participants younger than 18 years who did not have a baseline biopsy within 28 weeks of day 1 will not have a biopsy at the end of the open-label period. Upon completion of the open-label period, participants will enter the follow-up period (Part 4) unless they enter a long-term extension study.

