- d Vaccine series should be initiated at least 14 days prior to randomization; additional vaccines may be required at visit 6. Please see Section 8.2 for more details on vaccination requirements. Vaccination serum samples will be collected on the day of vaccination before receiving vaccinations on that visit. These samples will be analyzed to evaluate response to vaccinations in the event that the participant has a positive infection for *Streptococcus pneumoniae*. *Neisseria meningitidis*, or *Haemophilus influenzae*.
- A full physical examination is required at visits 1, 3 (week 1), 10 (week 26), and 16 (week 52). A full physical examination should also be conducted on the first day of open-label dosing, if that is not at the week 26 visit. Brief physical examinations, including weight (kg) and assessment of edema, will be conducted at all other visits noted. A symptom-driven physical examination may be performed at any time, at the investigator's discretion. Body height (cm) will be measured only during screening for adults but will be measured at screening and every 12 weeks throughout the study for adolescents; weight (kg) will be measured throughout study, during brief and full physical examinations for all participants. Both body weight and height will be assessed without shoes on; height will be measured using a calibrated stadiometer. Edema should be assessed at every visit.
- Renal biopsies will not be required for participants younger than 18 years provided that they have adequate previous renal biopsies to establish the diagnosis as per the central pathology laboratory.
- The week 26 renal biopsy need not occur on the same day as all other assessments for that visit. However, the week 26 triplicate FMU uPCR collections must occur before the renal biopsy. In addition, the week 26 biopsy must occur before the first visit of the open-label period at week 28. Participants younger than 18 years are not required to provide renal biopsies and may advance to the open-label period upon completion of all assessments for weeks 24 through 26 other than the renal biopsy.

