- h. The week 52 renal biopsy is optional for all participants. If performed it should be after collection of the week 48 24-hour urine and FMU samples, and not more than 8 weeks after the week 52 visit. In the event that a participant has a renal biopsy as part of their clinical management within this window, it may serve as the week 52 biopsy provided that it includes the required components for this study.
- Study drug will be self-administered by the participant or administered by their caregiver, after receiving appropriate training and sign-off by a research nurse (or other qualified personnel) in their first treatment week, as described in Section 9.5. Once qualified, the participant or caregiver should administer study drug at site visits (as done at home) on those days when a clinic visit occurs on a dosing day. If a home nurse is administering study drug on nonvisit days, the site staff may administer study drug on days of site visits.
- Between site visits, participants will be instructed to report any infusion site reactions to the study staff. Pump use safety will be reviewed by licensed health care professionals (eg, investigator or nurse) for each study drug administration at clinic visits and during at-home qualification.
- k. Vital signs should be measured a maximum of 2 hours before study drug infusion. On day 1 and on the first day of open-label dosing (week 26 or week 28, depending on whether a week 26 renal biopsy is required and when it is performed), vital signs should also be measured approximately 30 minutes to 1 hour after the first infusion of study drug dosing, timed from the completion of the study drug administration. Blood pressure and heart rate should be evaluated after the participant has been resting in a seated position for at least 5 minutes, except when they are supine or semireclined because of study procedures and/or AEs, or if deemed necessary by the investigator.
- ¹ FACIT-Fatigue, EQ-5D-5L, KDQOL, PGIC, and WPAI.
- m. The screening 24-hour urine collection may be done any time between screening visit 1 and screening visit 2. After week 1, collections should be within ±1 week of the visit (except for the week 24 collection, which cannot be earlier than week 24). Courier arrangements can be made to pick up the collection container from the participant, or the participant may return the container directly to the site.

Table 2: Schedule of Activities

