10.5.1. Renal Biopsies in Adults

For adult participants, a percutaneous biopsy will be performed at the visits indicated in the schedule of activities (Table 2).

A renal biopsy will be performed during screening to confirm diagnosis and eligibility, and to serve as the baseline renal biopsy. Once participant eligibility has been confirmed on the basis of the assessments from screening visit 1 and the initial 24-hour urine collection is complete as described in Section 10.2, the baseline renal biopsy may be conducted at any time during screening. A prior renal biopsy done within 28 weeks of randomization may be used for eligibility confirmation and serve as the baseline biopsy, if confirmed as adequate per central pathology review. Copies of prior renal biopsy reports will be requested for review by the central pathology laboratory. If a prior renal biopsy is used to establish eligibility and/or will serve as the baseline biopsy, images and/or slides from that biopsy will also be required. Tissue blocks and/or unstained slides may also be requested for staining at the central pathology laboratory.

Follow-up renal biopsies will be performed at week 26 and week 52. The week 26 biopsy is required for participants aged 18 years and older. The week 26 renal biopsy need not occur on the same day as all other assessments for that visit. However, the week 26 biopsy must occur after the week 26 triplicate FMU collections and before the first visit of the open-label period at week 28. The week 52 biopsy is optional. If performed it should be after collection of the week 48 24-hour urine and not more than 8 weeks after the week 52 visit.

In the event that a participant has a renal biopsy as part of their clinical management, biopsy samples should be reviewed by the central pathology laboratory and the results should be entered into the study database, if possible. If this biopsy includes the required components for this study and is collected within the window defined above, it may serve as the week 52 biopsy.

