13.3. Definition of Baseline, RCP, and OLP

For all evaluations unless otherwise noted, baseline is defined as the most recent non-missing measurement prior to the first administration of study drug. Baseline can be the same date as first dose, given the measurement is expected prior to first dose when only date information is available.

In by-visit summary tables, the baseline will be summarized using all available data, but also for each visit using only the baseline data from participants with available data at the visit; hence the mean change from baseline will equal the mean visit value – mean baseline value.

Throughout this document 'change from baseline' refers to the actual change from baseline (ie, visit value – baseline value).

The date when a participant receives first administration of OLP drug will be defined as the start date of the participant's OLP, and that date minus one day will be the end date of the participant's RCP.

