6.7. Analyses of Exploratory Efficacy Endpoints

All primary, key secondary, and additional secondary endpoints will be evaluated at Week 52 as exploratory efficacy endpoints (listed below as Section 6.7.1-11). Additional exploratory endpoints (listed below as Section 6.7.12-24) will also be evaluated.

6.7.1. Primary Efficacy Endpoint at Week 52

The analyses described in Section 6.4.1 (main analysis) and Section 6.4.3.2 (slope analysis) in the main SAP will be repeated at Week 52 using all available data through the Week 52 assessment based on the ITT Set.

ICE strategies will be the same as the first sensitivity analysis as specified in the main SAP Section 6.4.2 where missing data after the ICEs will be imputed implicitly within the MMRM in a hypothetical strategy under the assumption of MAR.

In addition, the observed values for uPCR will be summarized by treatment group and visit using the OLP set. Details on the baseline derivation for OLP set are specified in Section 13.

A shift table summary of FMU uPCR by categories (≥ 3 g/g, 1- ≤ 3 g/g, ≤ 1 g/g) will be generated. This also applies to the analysis for the RCP period.

For slope analysis, the mean rate of change in log-transformed uPCR will be compared between pegcetacoplan arm and control arm by use of a piecewise linear mixed effect model assuming time as continuous and piecewise linear ("piecewise slope model"). The analysis to be performed will be similar to what is described in the "slope model" except that a knot at the Week 26 visit will be added to both arms, which allows for the slope of log-transformed uPCR to differ between the two periods (RCP and OLP). Difference in slope will also be estimated by period.

6.7.2. The Proportion of Participants Who Meet the Criteria for Achieving a Composite Renal Endpoint at Week 52

The descriptive analysis described in Section 6.5.1.1 (main analysis) in the main SAP will be repeated at Week 52 based on the ITT Set by using available data through the Week 52 assessment.

ICE strategies will be the same as the main SAP where the endpoint status at or after the initiation of ICEs will be regarded as non-responder.

6.7.3. The Proportion of Participants with a Reduction of at least 50% from Baseline in uPCR at Week 52

The descriptive analysis described in Section 6.5.2.1 (main analysis) in the main SAP will be repeated at Week 52 based on the ITT Set by using available data through the Week 52 assessment.

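### The week 52 piecewise slope models change slope at the Week 26 visit, but the SAP starts the open-label period at the first open-label dose, which can be week 28

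*SAP*

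**What the plan says.** **Slope models.** Addendum 6.7.1 models log uPCR as piecewise linear in continuous time, as in the main slope model "except that a knot at the Week 26 visit will be added to both arms". Addendum 6.7.6 adds a Week 26 knot to the control arm only, for eGFR. Both label the two segments RCP and OLP and estimate a slope difference in each.

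**Definition of the periods.** SAP 13.3: "The date when a participant receives first administration of OLP drug will be defined as the start date of the participant's OLP". The RCP ends the day before. In SAP Table 5 the Week 26 window for unscheduled visits runs up to that date and the Week 28 window begins on it.

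**Dosing rule.** Protocol 6.1.3: "Open-label dosing will begin at the first visit after the week 26 renal biopsy for adults and any adolescents providing renal biopsies". It adds: "Open-label dosing for adolescents not providing renal biopsies should start at the week 26 visit". Protocol 10.5.1: "The week 26 biopsy is required for participants aged 18 years and older". The biopsy footnote to Table 2 says "the week 26 biopsy must occur before the first visit of the open-label period at week 28", and footnote k gives the first open-label day as "week 26 or week 28, depending on whether a week 26 renal biopsy is required and when it is performed".

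**Stated length.** The Synopsis gives the duration as "RCP: 26 weeks; open-label period: 26 weeks", and 6.1.3 describes a 26-week open-label period for all participants.

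**The concern.** The model's boundary between RCP and OLP is a fixed visit. The SAP's own boundary is a dated event that can fall at the next scheduled visit. For a placebo participant whose first open-label dose is at week 28, the time between the two visits belongs to the RCP under SAP 13.3 and to the OLP under the slope model.

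The week 28 observation is affected too. The note to Table 2 puts blood sampling before dosing, and Protocol 10.3 asks for first-morning urine before each visit. Such a participant's week 28 values would therefore normally precede any pegcetacoplan. The model nevertheless reads them as two weeks of treatment.

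In the pegcetacoplan arm the drug does not change at the knot, so only the placebo arm is misclassified. At stake are the placebo arm's two fitted slopes and the between-arm slope differences by period.

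**Working it through.** **1. Calendar.** From Table 2: week 26 = day 182 (±3), week 28 = day 196 (±3), week 52 = day 364.
- Stated open-label length: (364 − 182)/7 = 26.0 weeks, which reproduces the protocol's figure. The total also agrees: 10 + 26 + 26 + 8 = 70 weeks.
- With a week 28 start: (364 − 196)/7 = 24.0 weeks.
- Nominal gap: 196 − 182 = 14 days, or 14/182 = 7.7% of the segment after the knot.
- Gap allowing for visit windows: (196 − 3) − (182 + 3) = 8 days to (196 + 3) − (182 − 3) = 20 days.
- Visits after the knot: 28, 32, 36, 42, 48, 52. For a week 28 starter on placebo, one of the six is pre-dose.

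**2. Linear response.** Take a noise-free curve, flat until the true start s and then rising with slope 1: μ(t) = max(t − s, 0). Fit the planned form b0 + b1·t + b2·max(t − 26, 0) by least squares. The RCP slope is b1 (truth 0) and the OLP slope is b1 + b2 (truth 1). The uPCR visits are 0, 4, 8, 12, 16, 20, 24, 25, 26, 28, 32, 36, 42, 48, 52; the eGFR visits are the same without week 25. Using the nominal visit week follows SAP 17.2.3, where the sample code equates time with the visit number.

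| True start s | uPCR: OLP slope | uPCR: RCP slope | eGFR: OLP slope | eGFR: RCP slope |
|---|---|---|---|---|
| Week 27 | 0.964 | −0.017 | 0.967 | −0.021 |
| Week 28 | 0.928 | −0.034 | 0.935 | −0.041 |
| Week 28 + 3 days | 0.909 | −0.038 | 0.917 | −0.045 |

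There is no visit between weeks 26 and 28, so a half-and-half mix of week 26 and week 28 starters has the same mean curve as a week 27 start: at week 28, (2 + 0)/2 = 1 = 28 − 27. If 80% start at week 28, the OLP slopes are 0.942 (uPCR) and 0.948 (eGFR). With the knot at week 28 and everyone starting then, the OLP slope is 1.000.

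Weighting by a random intercept and slope covariance (assumed variances) gives the same values. With an assumed first-order autoregressive correlation of 0.8 per 4 weeks, the week 28 OLP slope is still 0.928 for both outcomes, but the RCP shift falls to −0.0135.

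**3. Response that levels off.** Assume a drop of 0.70 in log uPCR (0.92 − 0.22, the effect assumed in Protocol 12.1) that starts at week 28 and approaches its limit with time constant τ (assumed): −0.70·(1 − exp(−(t − 28)/τ)). The true average slope over weeks 28 to 52 is −0.70·(1 − exp(−24/τ))/24.

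| τ (weeks) | True slope per week | Knot 26: fitted, ratio to truth | Knot 28: fitted, ratio to truth | Knot 26 / knot 28 |
|---|---|---|---|---|
| 4 | −0.0291 | −0.0308, 1.06 | −0.0317, 1.09 | 0.97 |
| 8 | −0.0277 | −0.0287, 1.03 | −0.0301, 1.08 | 0.95 |
| 12 | −0.0252 | −0.0255, 1.01 | −0.0269, 1.07 | 0.95 |

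The Week 26 knot still gives a flatter slope than the week 28 knot, by 3 to 5%. Both are steeper than the true average, because a straight line is being fitted to a curve.

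**4. Size against noise.** With the protocol's SD of 0.88 and 62 per arm (124 enrolled according to the amendment summary, equal split assumed), the standard error of a mean log change is 0.88/√62 = 0.11. Seven percent of 0.70 is 0.05.

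**The case against.** The strongest reply is that little follows from the mismatch.

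- **Frequency.** The documents do not say how many participants start at week 28. The biopsy need not fall on the visit day, and urine should be collected before the visit, so a biopsy before the week 26 visit and a week 26 start are possible. This stands. Week 28 is the next scheduled visit when the biopsy falls on or after the week 26 visit, but calling it the usual start is an inference.
- **Direction.** A reader might infer that the fixed knot always biases the placebo arm's open-label slope toward no effect. Step 3 of the check shows that this needs a linear response, so the stronger reading is not supported.
- **Importance of this slope.** A reader might take it as the trial's estimate of the effect of starting pegcetacoplan. It is one of several. Addendum 6.7.13 pools the regimens for a before-and-after eGFR slope comparison and counts the placebo arm's RCP data as pre-treatment, which follows the SAP 13.3 date. Addendum 6.7.1 and 6.7.6 also summarize uPCR and eGFR in the OLP set from a baseline before OLP start.
- **Exposure.** A reader might infer that 26 weeks of active treatment will be credited to every placebo participant. SAP 5.6 computes treatment duration from infusion dates, Addendum 5.6 repeats this for the OLP, and the Synopsis presents its 52-week treatment total as a maximum.
- **Age groups.** Adult and adolescent slopes could differ in timing, but Addendum 6.7.1 does not repeat the subgroup analyses, so no such comparison is planned.

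None of this removes the mismatch between the knot and SAP 13.3.

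**Conclusion.** The point holds as an internal inconsistency of small consequence. Two of the three week 52 slope analyses (Addendum 6.7.1 and 6.7.6) use a period boundary that differs from the SAP's definition for anyone whose open-label dosing begins after the Week 26 visit.

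Under a linear response the placebo arm's fitted OLP slope is about 0.93 of the true value if all start at week 28, and 0.96 to 0.97 if the average start is week 27. The RCP slope then moves by about 3 to 4% of the OLP slope in the opposite direction for an all-week-28 start, and by less under strong serial correlation. If the response levels off, the net direction depends on the curve. The share starting at week 28 and the shape of the response are assumptions.

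The analyses are exploratory, and Addendum 6.2 rules out formal testing of OLP data. The week 26 primary analysis is unaffected. Adverse events are assigned to periods by the actual OLP date.

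Separately, a 26-week open-label period stated without exception does not fit a week 28 start. The protocol passages need reconciling; this does not enter the slope model.

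**What to change.** In Addendum 6.7.1 and 6.7.6, set the knot at each participant's OLP start date as defined in SAP 13.3, and use actual study day as the time variable. State a rule for participants in the ITT set who never receive OLP drug; for example, all their data could stay in the RCP segment. Keep the Week 26 knot as a sensitivity analysis. Because a curved response matters as much as the knot date, the report should describe the fitted slopes as averages under assumed linearity.

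Protocol 6.1.3, 6.3, Table 2 and the stated 26-week open-label period should be reconciled, including what applies between the week 26 visit and the first open-label dose. No dosing rule or duration is proposed here.

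The cost is a wording change and slightly longer code with participant-specific knots. The date is already derived and no new data are needed.

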6.7.16. Time to 50% Reduction in uPCR with a Stable or Improved eGFR

The analysis described in Section 6.7.6 in the main SAP will be repeated based on the ITT set using all available data through the Week 52 assessment. For event-free survival, present the timepoints of week 12, week 24, week 36, and week 48.

6.7.17. Time to Normalization for Selected Parameters for Participants in Whom the Parameter is Abnormal at Baseline

The analysis described in Section 6.7.7 in the main SAP will be repeated based on the ITT set using all available data through the Week 52 assessment. For event-free survival, present the timepoints of week 12, week 24, week 36, and week 48.

Note for time to normalization of serum C3, the normalization is not applicable for this endpoint hence the analysis is revised as time to serum C3 levels being greater than or equal to the lower limit of normal (LLN). This also applies to the analysis for the RCP period.

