6.7.5. Time to 50% Reduction in uPCR With a Stable or Improved eGFR

Time to 50% reduction in uPCR with a stable or improved eGFR (a.k.a., achieving the composite renal endpoint as defined in Section 6.5.1) will be summarized using ITT set with the Kaplan-Meier method (Kaplan and Meier 1958), using plots and presentation of median (and 95% CIs) for time-to-event. Participants who did not have the event at or prior to Week 26 in study will be censored at the minimum of the last date of contact or their treatment discontinuation date, or their Week 26 visit or first dose date+182 if Week 26 is missing. Participants who were randomized but did not receive any treatment will be censored at Day 1. Time to vent (or censor) will be calculated as date of event (or censor date) – Day 1 date +1. Event rates at week 12 and week 26 will also be presented in the summary tables. Comparisons between treatment groups will be done using Cox proportional hazard models (Cox 1976) stratified by disease type (C3G vs IC-MPGN) and stratification factors, and adjusted for baseline eGFR values and baseline log-transformed uPCR values. The hazard ratio, 95% CI, and p-value will be presented for the pegcetacoplan group over placebo group.

A data listing for each participant's time to achieve 50% reduction in uPCR with a stable or improved eGFR will be provided using ITT set.

6.7.6. Time to Normalization for Selected Parameters for Participants in Whom the Parameter is Abnormal at Baseline

For parameters serum C3, uPCR (measured by triplicate FMU), serum albumin, and blood pressure (both SBP and DBP), time to normalization (in weeks) will be summarized using ITT set with the Kaplan-Meier method, using plots and presentation of median (and 95% CIs) for time-to-event. Participants who did not have the event at or prior to Week 26 in study will be censored at the minimum of the last date of contact or their treatment discontinuation date, or their Week 26 visit or first dose date+182 if Week 26 is missing. Participants who were randomized but did not receive any treatment will be censored at Day 1. Time to vent (or censor) will be calculated as date of event (or censor date) – Day 1 date +1. Event rates at week 12 and week 26, as well as p-values from the log-rank test (stratified by disease type and stratification factors) will also be presented in the summary tables. The analyses will be based on participants whose test result being abnormal at baseline.

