7. SAFETY ANALYSIS

7.1. Adverse Events

Further detail is provided in the main SAP Section 7.1. The same summaries for RCP as in the main SAP will be repeated for OLP (except for rejection episodes and graft loss where only descriptive summaries are required at Week 52) using all available data through the Week 52 assessment.

Besides the AESI summaries as per the CRF form checkbox question "Is this event an AESI?", additional summaries for the AEs of special search will be provided based on the special search teams provided by Apellis safety team, more specifically:

- Infections: SOC-infections and infestations; HLGT- Bacterial infectious disorders, HLGT- Fungal infectious disorders, HLGT- Viral infectious disorders
- Hypersensitivity: SMQ-Hypersensitivity (narrow)
- Acute Kidney Injury: SMQ- Acute Renal Failure (narrow)
- Thrombocytopenia: HLT- Thrombocytopenias, PT-Platelet count decreased, PT-Plateletcrit decreased, PT-Platelet count abnormal

AEs will be summarized by treatment groups and period. Data will be presented in 5 columns: (1) Pegcetacoplan group's RCP results; (2) Pegcetacoplan group's OLP results; (3) Placebo group's OLP results; (4) OLP results combined (in other words, combining columns 2 and 3); (5) for all results since Pegcetacoplan injection (in other words, combining columns 1 and 4). The classification of AEs in the RCP or OLP will be based on the AE start date compared to the RCP/OLP threshold as defined in the main SAP Section 13.3.

For AE summaries that relate to rejection episodes, in addition to the preferred terms specified in the main SAP, one additional preferred term of "Transplant rejection" is also added based on Apellis team review.

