10. IMMUNOGENICITY

Refer to main SAP Section 10 for further details of the analysis.

The same summaries for RCP as in the main SAP will be repeated using all available data through the Week 52 assessment.

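### The SAP addendum repeats the pegcetacoplan-versus-placebo time-to-event comparisons through week 52 with no allowance for the placebo arm's switch to pegcetacoplan, and leaves the week 26 censoring rule unreplaced

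*SAP*

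**What the plan says.** Main SAP 6.7.5 analyses time to the composite renal response by Kaplan-Meier and a stratified Cox model: "The hazard ratio, 95% CI, and p-value will be presented for the pegcetacoplan group over placebo group". Main SAP 6.7.6 analyses time to normalization by Kaplan-Meier with a stratified log-rank p-value and no hazard ratio. Both run from Day 1. Both censor participants without an event at the earliest of last contact, treatment discontinuation, and the week 26 visit (or first dose plus 182 days if that visit is missing).

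Addendum 6.7.16 states that the analysis in main SAP 6.7.6 "will be repeated based on the ITT set using all available data through the Week 52 assessment". For event-free survival it asks to "present the timepoints of week 12, week 24, week 36, and week 48". Addendum 6.7.17 does the same but cites main SAP 6.7.7.

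The ITT set keeps participants in their randomized arm (main SAP 4.2). Under Protocol 6.1.3, "participants from both groups will proceed to the 26-week open-label period, in which all participants will be treated with pegcetacoplan twice weekly". Open-label dosing starts at the first visit after the week 26 biopsy for those biopsied, and at week 26 for adolescents who are not.

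Elsewhere the addendum does allow for the switch. It puts a knot at week 26 in the uPCR slope model (both arms, 6.7.1) and in the eGFR slope model (control arm, 6.7.6). It treats placebo-period eGFR as pre-treatment data in 6.7.13. For adverse events (7.1), "Data will be presented in 5 columns", split by arm and period.

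**The concern.** From the switch onward both randomized arms take the same drug. A response on pegcetacoplan in a participant randomized to placebo is still counted as a placebo-arm event. Addendum 6.7.16 and 6.7.17 do not censor at the switch, split follow-up by period, use time-varying treatment, or relabel the contrast as immediate versus delayed start. A hazard ratio headed pegcetacoplan over placebo would therefore average two different comparisons, and the weeks 36 and 48 placebo estimates would not describe placebo.

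Two further defects prevent these sections from being programmed as written. The inherited censoring ends follow-up by week 26, which cannot be squared with readouts at weeks 36 and 48. The cross-references also point to the wrong sections: main SAP 6.7.6 is time to normalization and 6.7.7 is the macrophage count.

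Addendum 10 has a related descriptive gap. For antidrug antibodies (ADA) it says "The same summaries for RCP as in the main SAP will be repeated using all available data through the Week 52 assessment", with no period split, so the placebo column would mix positives arising on placebo with positives arising on pegcetacoplan.

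**Working it through.** **1. The plan's own figure.** The only design calculation is for the primary endpoint (main SAP 3.4): difference 0.92 − 0.22 = 0.70, SD 0.88, one-sided 0.025, 90% power. Per arm, 2 × (1.960 + 1.282)² × 0.88² / 0.70² = 33.2, so 34 per arm and 68 in total. The stated 70 gives 90.7% power by the t-test, and 70/0.90 = 77.8 rounds up to 78. The design reproduces. It contains no event rate for the time-to-event endpoints, so what follows is illustration.

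**2. Which analysis is repeated.** By title, Addendum 6.7.16 matches main SAP 6.7.5 and Addendum 6.7.17 matches main SAP 6.7.6. The same one-section shift appears in Addendum 6.7.19 to 6.7.21. The hazard ratio therefore belongs to 6.7.16; for 6.7.17 the affected statistic is the log-rank p-value.

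**3. Response rates implied by the planning inputs** (at least 50% uPCR reduction at week 26, eGFR component ignored, log ratio normal):
- pegcetacoplan: Φ((ln 0.5 + 0.92)/0.88) = Φ(0.258) = 60.2%
- placebo: Φ((ln 0.5 + 0.22)/0.88) = Φ(−0.538) = 29.5%

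**4. Constant hazards to week 26.** −ln(1 − 0.602) = 0.921 and −ln(1 − 0.295) = 0.350 over 26 weeks. Hazard ratio = 0.921/0.350 = 2.63.

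**5. The placebo arm after the switch**, if it takes on the pegcetacoplan hazard of 0.921/26 = 0.0354 per week:
- week 48: 1 − 0.705 × exp(−0.0354 × 22) = 67.7% with an event, against 1 − exp(−0.350 × 48/26) = 47.6% had it stayed on placebo
- week 52: 1 − 0.705 × 0.398 = 71.9%, so (71.9 − 29.5)/71.9 = 59% of its events come after the switch

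**6. Cox hazard ratio through week 52**, simulated with 10,000 per arm. The columns give the hazard after week 26 in the original pegcetacoplan arm, relative to its earlier value.

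| Assumed week 26 rates | HR to week 26 (formula) | Unchanged | Halved | Quartered |
|---|---|---|---|---|
| 60.2% vs 29.5% (planning inputs) | 2.63 | 1.72 | 1.37 | 1.25 |
| 60% vs 10% | 8.7 | 2.38 | 1.88 | 1.68 |
| 50% vs 5% | 13.5 | 2.41 | 1.76 | 1.58 |

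For the planning inputs with no switch, the simulated ratio through week 52 stays near 2.6. Over weeks 26 to 52 alone, with the switch, it is about 1.0, 0.5 and 0.27 in the three columns. With 62 per arm (124 enrolled, 1:1), times grouped to visits and Efron ties, the planning inputs give medians of 1.75 (unchanged) and 1.45 (halved). The range is therefore about 1.25 to 1.75.

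**The case against.** The strongest reply is that nothing of weight is lost. The drug-versus-placebo hazard ratio is already given by main SAP 6.7.5 with follow-up ended by week 26. Addendum Section 1 says its analyses do not replace earlier ones unless so specified, the week 52 endpoints are exploratory, and Addendum 6.2 rules out formal testing of open-label data. All of this stands and limits the harm. It does not make the repeated statistic interpretable. Neighbouring week 52 items repeat only the descriptive analysis; these two repeat the analysis without that limit, and so bring in p-values that sit badly with Addendum 6.2.

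It can also be said that the hazard ratio in 6.7.16 is an inference, because the section actually cited has none. That is true, and the reading by title should be stated openly. Likewise, if the week 26 censoring were kept literally, the comparison would stay clean, but it would contradict the request for data through week 52 and the later readouts. Either way the text needs repair.

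A reader might infer several stronger things that the documents do not support:
- **That the drug effect would be understated several-fold.** This holds only under assumed low placebo rates. The planning inputs give roughly 2.63/1.75 = 1.5-fold to 2.63/1.25 = 2.1-fold.
- **That the larger pool of placebo non-responders biases the hazard ratio.** The Cox model conditions on those still at risk. With equal hazards after the switch, the late-period ratio is about 1.0, which is dilution. Reversal needs the late hazard in the original pegcetacoplan arm to fall.
- **That the whole placebo arm switches exactly at week 26.** Only those entering the open-label period switch, many of them after the biopsy. Events before the switch remain a valid comparison.

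**Conclusion.** The point holds as a should-fix on an exploratory analysis. As written, Addendum 6.7.16 and 6.7.17 produce between-arm statistics through week 52 that mix two treatment contrasts, under a censoring rule that conflicts with their own readouts. The primary conclusion, the week 26 time-to-event results and type I error are untouched.

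The size is illustrative. On the SAP planning inputs, a hazard ratio of about 2.6 at week 26 becomes about 1.25 to 1.75 through week 52 with no change in the drug's effect in the randomized period. This rests on log-normal uPCR change, no eGFR component, constant hazards within each period, and switched participants taking on the initial pegcetacoplan hazard. The ratio moved toward 1 in every switch scenario tried; the amount depends on the placebo rate assumed. The ADA point is secondary and descriptive, since no between-arm ADA test is planned.

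**What to change.** In Addendum 6.7.16 and 6.7.17:
1. Limit the between-arm Cox hazard ratio and log-rank test to data censored at the end of the randomized controlled period, as defined in main SAP 13.3.
2. Present the week 52 Kaplan-Meier curves descriptively, labelled immediate versus delayed start.
3. State the week 52 censoring rule in place of the inherited week 26 one.
4. Correct the cross-references to main SAP 6.7.5 and 6.7.6.

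In Addendum 10, split the ADA summaries by period, as is done for adverse events.

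Restarting the placebo clock at an open-label baseline is not needed. It would redefine both the event (reduction from the week 24 to 26 average) and the denominator (abnormal at open-label start).

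The cost is addendum wording and reprogramming of a few exploratory tables, with no new data. The downside is that there would be no single 52-week between-arm hazard ratio.
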